9.3.2 Pharmacokinetic Statistical Methodology

No formal statistical analyses are planned.

9.4 Safety and Tolerability Assessments

9.4.1 Adverse events

Where changes in severity are recorded in the Case Report Form (CRF), each separate severity of the AE will be reported in the listings, only the most severe will be used in the summary tables. A pre-existing condition is defined as an AE that starts before the participant has provided written informed consent and is ongoing at consent. A non-treatment emergent AE is defined as an AE which starts after informed consent but prior to dosing. A treatment-emergent AE is defined as an AE which occurs postdose or which is present prior to dosing and becomes more severe postdose.

All AEs will be listed. Treatment-emergent AEs will be summarized by part, severity and relationship to the study drug. The frequency (the number of AEs, the number of participants experiencing an AE and the percentage of participants experiencing an AE) of treatment-emergent AEs will be summarized by treatment, Medical Dictionary for Regulatory Activities (MedDRA) version 24.0 system organ class and preferred term. The summary and frequency AE tables will be presented for all causalities and those considered related to the study drug by the investigator. Any serious adverse events (SAEs) will be listed.

Discontinuations due to AEs will be listed.

9.4.2 Concomitant medication

Concomitant medication will be coded using the World Health Organization (WHO) drug dictionary (Version MAR21B3). Concomitant medication will be listed.

9.4.3 Clinical laboratory parameters

All clinical chemistry and hematology data will be summarized by parameter and part, and listed. Urinalysis data will be listed. Additionally, clinical chemistry, hematology and urinalysis data outside the reference ranges will be listed and flagged on individual participant data listings.

9.4.4 Vital signs

Vital signs data will be summarized by treatment together with changes from baseline, where baseline is defined as the Day 1 predose assessment. Figures of mean vital signs and mean changes from baseline profiles will be presented by part.

Values for individual participants will be listed.

9.4.5 Electrocardiogram (ECG)

ECGs will be performed for safety monitoring purposes only and will not be presented. Any clinically significant findings from ECGs will be reported as an AE.

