8.2.3. Electrocardiograms

Single 12-lead ECG will be obtained as outlined in the SoA (see Section 1.3) using an ECG machine that automatically calculates the heart rate and measures PR, QRS, QT, and QTc intervals.

Electrocardiograms must be recorded before collecting any blood samples. Participants must be supine for approximately 5 to 10 minutes before ECG collection and remain supine but awake

during ECG collection. Electrocardiograms may be obtained at additional times, when deemed clinically necessary. All ECGs recorded should be stored at the investigational site.

Electrocardiograms will be interpreted by the investigator or qualified designee at the site as soon after the time of ECG collection as possible, and, ideally, while the participant is still present. This interpretation is to determine whether the participant meets entry criteria at the relevant visit(s) and for immediate participant management, should any clinically relevant findings be identified.

If a clinically significant finding is identified (including, but not limited to, changes in QT/QTc interval from baseline) after enrollment, the investigator will determine if the participant can continue in the study. The investigator, or qualified designee, is responsible for determining if any change in participant management is needed and must document her review of the ECG printed at the time of collection. Any new clinically relevant finding should be reported as an AE.

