9.3.1.2. Statistical Evaluation of Safety

Safety parameters that will be assessed include clinical laboratory parameters, vital signs, and ECG parameters. Additional analysis will be performed if warranted upon review of the data.

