3. INTRODUCTION

This SAP has been developed after review of the Clinical Study Protocol (final version dated 25 May 2021), and Protocol Amendment (a) (final version dated 25 June 2021).

This SAP describes the planned analysis of the safety, tolerability and pharmacokinetic (PK) data from this study. A detailed description of the planned TFLs to be presented in the clinical study report (CSR) is provided in the accompanying TFL shell document.

The intent of this document is to provide guidance for the statistical and PK analyses of data. In general, the analyses are based on information from the protocol, unless they have been modified by agreement with Eli Lilly and Company. A limited amount of information concerning this study (e.g., objectives, study design) is given to help the reader's interpretation. For open-label studies, this SAP must be signed off prior to first participant visit for this study. When the SAP and TFL shells are agreed upon and finalized, they will serve as the template for this study's CSR.

This SAP supersedes the statistical considerations identified in the protocol; where considerations are substantially different, they will be so identified. If additional analyses are required to supplement the planned analyses described in this SAP, they may be performed and will be identified in the CSR. Any substantial deviations from this SAP will be agreed upon with Eli Lilly and Company and identified in the CSR. Any minor deviations from the TFLs may not be documented in the CSR.

This SAP is written with consideration of the recommendations outlined in the International Conference on Harmonisation (ICH) E9 Guideline entitled Guidance for Industry: Statistical Principles for Clinical Trials¹ and the ICH E3 Guideline entitled Guidance for Industry: Structure and Content of Clinical Study Reports².

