5. STUDY DESIGN

5.1 Overall Design

Study JZLE is an open-label, 2-part, disposition and absolute bioavailability study of [¹⁴C]-LY3484356 in healthy females with nonchildbearing potential at a single Phase 1 clinical research unit (CRU). In Part 1, it is planned that up to 6 participants may be enrolled to ensure that at least 4 participants complete the study or have evaluable PK data. In Part 2, it is planned that up to 8 participants may be enrolled to ensure that at least 6 participants complete the study or have evaluable PK data for both treatments (oral and IV). Participants in Part 1 will not participate in Part 2, nor will participants in Part 2 participate in Part 1. Part 1 and Part 2 are independent of each other and do not need to be conducted in sequential order.

Safety assessments, including adverse events (AEs), clinical laboratory tests, vital signs, and electrocardiogram (ECGs), and blood sampling for PK, will be performed.

A schematic of the study designs are presented in [Figure 1](#) (Part 1) and [Figure 2](#) (Part 2).

CCI

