11. CHANGES FROM THE PROTOCOL SPECIFIED STATISTICAL ANALYSES

There were no changes from the protocol specified statistical analyses.

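### Does leaving ECG data out of the SAP's outputs break the protocol's statement that ECG parameters will be assessed?

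*SAP*

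**What the plan says.** Protocol 9.3.1.2 has two sentences. The first is "Safety parameters that will be assessed include clinical laboratory parameters, vital signs, and ECG parameters". The second is "Additional analysis will be performed if warranted upon review of the data". Neither specifies a listing, a summary, a change from baseline or a particular interval.

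Protocol 8.2.3 calls for a single 12-lead ECG at scheduled times, "using an ECG machine that automatically calculates the heart rate and measures PR, QRS, QT, and QTc intervals". The site interprets the tracing to check entry criteria and to manage the participant there and then. New clinically relevant findings become adverse events, and the tracings are kept at the site.

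In the SAP, section 5.1 names ECGs among the safety assessments to be performed ("Safety assessments, including adverse events (AEs), clinical laboratory tests, vital signs, and electrocardiogram (ECGs"). Sections 9.4.3 and 9.4.4 plan summaries and listings for chemistry, hematology and vital signs. Section 9.4.5 states that "ECGs will be performed for safety monitoring purposes only and will not be presented" and sends clinically significant findings to adverse event reporting. Section 3 makes the SAP supersede the protocol's statistical considerations and adds that "where considerations are substantially different, they will be so identified". Section 11 reads: "There were no changes from the protocol specified statistical analyses".

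**The concern.** One sentence in the protocol's statistics section puts three parameter sets on an equal footing. The SAP gives two of them tables and listings and gives the third nothing. SAP 3 undertakes to identify substantial differences, and SAP 11 identifies none. Someone who reads SAP 11 alone would not learn that ECG output had been left out.

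What would be lost is any view of the interval values themselves. PR, QRS, QT and QTc are measured by the machine, yet under SAP 9.4.5 only a finding that the investigator judges important in an individual reaches the report. A small shift shared by several participants would leave no trace. The *no changes* statement would also be wrong if the protocol had promised ECG output.

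**Working it through.** No plan figure needs reproducing; the question is how the texts fit together.

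**1. What the protocol commits to.** The operative word in 9.3.1.2 is *assessed*. The section specifies no output for any of the three sets and leaves further analysis to review of the data. The SAP's choice to tabulate laboratory data and vital signs does not turn the same word into a promise of ECG tables.

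**2. What assessing an ECG means here.**

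| Point | Protocol 8.2.3 | SAP 9.4.5 |
|---|---|---|
| Purpose | Entry criteria and immediate management | Safety monitoring only |
| Who judges | Investigator or qualified designee at the site | Not restated |
| Route to the report | New clinically relevant findings as adverse events; changes in QT/QTc from baseline are given as an example of a significant finding | Clinically significant findings as adverse events |
| Interval tables | None mentioned | Excluded explicitly |

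The two sections describe the same process. SAP 9.4.1 then lists all adverse events and summarizes the treatment-emergent ones, so ECG findings of clinical weight do reach the report.

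**3. Whether another SAP rule restores a listing.** SAP 9.4.8 lists safety assessments that the section does not otherwise cover; ECG is covered by 9.4.5, so 9.4.8 does not apply. SAP 9.1 promises listings of all databased data, but the documents do not say that ECG intervals are databased; Protocol 8.2.3 says only that the tracings are stored at the site. There are two cases:

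- Not databased: SAP 9.1 is not engaged, and there is no conflict.
- Databased: the general rule in 9.1 meets the specific rule in 9.4.5, and the specific one would normally govern.

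In neither case does a summary arise by default, because 9.1 confines summaries to data for which the SAP details them.

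**4. Whether SAP 11 is false.** It would be false only if the protocol had specified an ECG analysis that the SAP removed. On step 1 it had not. SAP 3 asks that substantial differences be identified without saying where, and 9.4.5 states the exclusion in its own numbered section.

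**5. What tables would add.** Planned enrollment is up to 6 in Part 1 and up to 8 in Part 2, so 6 + 8 = 14 in all, plus any replacements. ECGs are single recordings after a single-dose regimen, with no control group, and SAP 9.4.9 plans no inference. The schedule of activities is redacted, so it cannot be seen whether routine postdose ECGs exist. If there are none, a change-from-predose table would be empty. The stated safety endpoint in both parts is a summary of treatment-emergent adverse events, which such tables would not touch.

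**The case for a change.** The best argument on the other side concerns where the sentence sits. Protocol 9.3.1.1 covers clinical evaluation and adverse events; 9.3.1.2 is headed as statistical evaluation. If adverse event reporting were enough to satisfy 9.3.1.2, naming ECG parameters there would add nothing. The SAP itself treats the other two sets in the sentence as needing output. The adverse event route also depends on judgement about individuals and cannot show a common small shift. The routes for extra work, in Protocol 9.3.1.2 and in SAP 3 (additional analyses: "they may be performed and will be identified in the CSR"), are discretionary. Vital signs do not fill the gap either: supine pulse rate is a separate measurement from ECG heart rate, and nothing visible shows that the two are taken at the same times.

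Part of this stands. The heading does lean toward a statistical reading, and a sentence in SAP 9.4.5 or SAP 11 saying that ECGs are assessed clinically and not tabulated would have closed the question. That is housekeeping. It does not show that a promised analysis was dropped, because none was specified. The loss of group-level interval data is real but small: a shared shift in single, uncontrolled recordings from groups of up to 6 and up to 8 could not be attributed to the drug with any confidence. Against that, tabulating the values would mean transferring and checking them from site records, and possibly adding data capture, to reverse a deliberate reporting choice.

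**Conclusion.** No change to the plan follows. The SAP's treatment of ECGs agrees with the use that Protocol 8.2.3 gives them, the exclusion is stated openly, and the protocol specifies no ECG output that the SAP fails to deliver. The residue is a missing cross-reference between SAP 9.4.5 and SAP 11. It affects no estimate, no conclusion and neither part's safety endpoint, for up to 14 planned participants plus replacements.

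This rests on reading *assessed* in Protocol 9.3.1.2 as clinical review with adverse event reporting, which Protocol 8.2.3 supports but the section heading does not settle. It also rests on what can be seen: the schedule is redacted, the table and listing shells are a separate document, and the text does not say whether intervals are databased. If they are, the analyst has only to apply the specific ECG rule over the general listing rule in SAP 9.1, and again no result changes.

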9.4.6 Product Acceptability and Palatability Assessments

Participants in Part 1 will be asked to provide responses to questions designed to assess the acceptability and palatability of the solution after treatment administration. The questionnaire will assess the participant's experience relating to the taste, mouthfeel, and aftertaste of the solution in the oral cavity. The questionnaire will be completed by the participant immediately after administration of the solution i.e. within 5 minutes of dosing.

These data will be summarized by part, and listed.

9.4.7 Hepatic Monitoring

Close hepatic monitoring

If a participant who had normal or near normal baseline alanine aminotransferase (ALT), aspartate aminotransferase (AST), alkaline phosphatase (ALP), total bilirubin (TBL) (i.e., $<1.5 \times$ upper limit of normal [ULN]), experiences elevated ALT $\geq 3 \times$ ULN, AST $\geq 3 \times$ ULN, ALP $\geq 2 \times$ ULN, or TBL $\geq 2 \times$ ULN, laboratory tests should be repeated within 48 to 72 hours, including ALT, AST, ALP, TBL, direct bilirubin, gamma-glutamyltransferase, and creatinine kinase to confirm the abnormality and to determine if it is increasing or decreasing.

In participants enrolled with elevated baseline ALT, AST, ALP or TBL ($\geq 1.5 \times$ ULN), the thresholds for close monitoring are AL T $\geq 2 \times$ baseline, AST $\geq 2 \times$ baseline, AL P $\geq 2 \times$ baseline, or TBL $\geq 1.5 \times$ baseline.

At a minimum, this evaluation should include physical examination and a thorough medical history, including symptoms, recent illnesses, (for example, heart failure, systemic infection, hypotension, or seizures), recent travel, history of concomitant medications (including over-the-counter), herbal and dietary supplements, history of alcohol drinking and other substance abuse.

If the abnormality persists or worsens, clinical and laboratory monitoring, and evaluation for possible causes of abnormal liver tests should be initiated by the investigator in consultation with the Lilly-designated medical monitor.

Comprehensive hepatic evaluation

If a study participant, who had baseline ALT, AST, ALP, TBL $<1.5 \times$ ULN, experiences elevated ALT $\geq 5 \times$ ULN, AST $\geq 5 \times$ ULN, ALP $\geq 3 \times$ ULN, TBL $\geq 2 \times$ ULN, or elevated ALT, AST $\geq 3 \times$ ULN with hepatic signs/symptoms (severe fatigue, nausea, vomiting, right upper quadrant abdominal pain, fever, rash, and/or eosinophilia $>5\%$), a comprehensive evaluation should be performed to search for possible causes of liver injury.

In participants who had elevated baseline ALT, AST, ALP, or TBL ($\geq 1.5 \times$ ULN), the thresholds for performing this evaluation are ALT $\geq 3 \times$ baseline, AST $\geq 3 \times$ baseline, ALP $\geq 2 \times$ baseline, TBL $\geq 2 \times$ baseline, or ALT, AST $\geq 2 \times$ baseline with hepatic signs/symptoms.

At a minimum, this evaluation should include physical examination and a thorough medical history, as outlined above, as well as tests for prothrombin time-international normalized ratio, viral hepatitis A, B, C, E, tests for autoimmune hepatitis, and an abdominal imaging study (for example, ultrasound or computed tomography scan).

Additional hepatic data collection in participants who have abnormal liver tests during the study

Additional hepatic safety data collection should be performed in participants who meet 1 or more of the following 5 conditions:

1. Elevation of serum ALT to $\geq 5 \times$ ULN on 2 or more consecutive blood tests (if baseline ALT $< 1.5 \times$ ULN)
 - In participants with baseline ALT $\geq 1.5 \times$ ULN, the threshold is ALT $\geq 3 \times$ baseline on 2 or more consecutive tests
2. Elevation of TBL to $\geq 2 \times$ ULN (if baseline TBL $< 1.5 \times$ ULN)
 - In participants with baseline TBL $\geq 1.5 \times$ ULN, the threshold should be TBL $\geq 2 \times$ baseline
3. Elevation of serum ALP to $\geq 2 \times$ ULN on 2 or more consecutive blood tests (if baseline ALP $< 1.5 \times$ ULN)
 - In participants with baseline ALP $\geq 1.5 \times$ ULN, the threshold is ALP $\geq 2 \times$ baseline on 2 or more consecutive blood tests
4. Hepatic event considered to be an SAE
5. Discontinuation of the investigational product due to a hepatic event.

Where applicable, the following will be presented. The participants' liver disease history and associated person liver disease history data will be listed. Any concomitant medications that have potential for hepatotoxicity, including acetaminophen will be listed. Results from any hepatic

monitoring procedures, such as a magnetic resonance elastography scan, and biopsy assessments will be listed, if performed.

Hepatic risk factor assessment data will be listed. Liver related signs and symptoms data will be summarized by treatment and listed. Alcohol and recreational drug use data will also be listed.

All hepatic chemistry, hematology, coagulation, and serology data will be listed. Values outside the reference ranges will be flagged on the individual participant data listings.

9.4.8 Other assessments

All other safety assessments not detailed in this section will be listed but not summarized or statistically analyzed.

9.4.9 Safety and Tolerability Statistical Methodology

No inferential statistical analyses are planned.

10. INTERIM ANALYSES

No interim analyses are planned for this study. If an unplanned interim analysis is deemed necessary for reasons other than a safety concern, the protocol and SAP must be amended.

11. CHANGES FROM THE PROTOCOL SPECIFIED STATISTICAL ANALYSES

There were no changes from the protocol specified statistical analyses.

13. DATA PRESENTATION

13.1 Derived Parameters

Individual derived parameters (e.g. PK parameters) and appropriate summary statistics will be reported to three significant figures. Observed concentration data, e.g. C_{max} , should be reported as received. Observed time data, e.g. t_{max} , should be reported as received. N and percentage values should be reported as whole numbers. Median values should be treated as an observed parameter and reported to the same number of decimal places as minimum and maximum values.

13.2 Missing Data

Missing data will not be displayed in listings.

13.3 Insufficient Data for Presentation

Some of the TFLs may not have sufficient numbers of participants or data for presentation. If this occurs, the blank TFL shell will be presented with a message printed in the center of the table, such as, "No serious adverse events occurred for this study."

